ICH E6	International Conference on Harmonisation Guidance for Industry, Good Clinical Practice: Consolidated Guidance
ICMJE	International Committee of Medical Journal Editors
IRB	Institutional Review Board
ISO 14155:2011	International Organization for Standardization Good Clinical Practices for Clinical
MedDRA	Medical Dictionary for Regulatory Activities
PI	Principal Investigator
QC	Quality Control
SAE	Serious Adverse Event
SAP	Statistical Analysis Plan
SC	Subcutaneous
SLIQ	Simple Lifestyle Indicator Questionnaire
US	Ultrasound
UP	Unanticipated Problem

STATEMENT OF COMPLIANCE

The trial will be carried out in accordance with Good Clinical Practice (GCP) as required by the following:

- United States (US) Code of Federal Regulations (CFR) applicable to clinical studies (45 CFR Part 46, 21 CFR Part 50, 21 CFR Part 56, 21 CFR Part 312, and/or 21 CFR Part 812) or equivalent local regulatory regulations or guidelines
- ICH E6
- ISO 14155:2011

All key personnel (all individuals responsible for the design and conduct of this trial) have completed Human Subjects Protection Training.

I agree to ensure that all staff members involved in the conduct of this study are informed about their obligations in meeting the above commitments.

Principal Investigator: _____

[figure not shown]
Print/Type Name

Signed: _____ Signature Date: _____

PROTOCOL SUMMARY

TITLE	Clinical Evaluation of the Safety and Efficacy of a 1060nm Diode Laser for Non-Invasive Fat Reduction of the Abdomen
SUMMARY	Open-label, baseline-controlled, evaluator-blind multi-center study evaluating a 1060 nm diode laser for non-invasive fat reduction of the abdomen. The study will enroll up to 50 subjects requesting non-invasive lipolysis of the abdomen. Each subject will receive a single study treatment. Subjects will be followed at six weeks and twelve weeks post-treatment. Twelve week outcomes will be compared to baseline.
OBJECTIVE	The objective of this clinical study is to assess the safety and efficacy of using a 1060 nm diode laser for non-invasive fat reduction of the abdomen.
ENDPOINT	
Primary endpoints
 
Photographic evaluation by independent, blinded reviewers with correct identification of pre-treatment baseline images when compared to post-treatment images taken at twelve weeks 
Secondary endpoints
 
To determine the change in thickness of the adipose layer as measured by ultrasound (US) at twelve weeks post-treatment as compared to baselineTo determine the change in abdominal circumference at twelve weeks post-treatment as compared to baselineTo assess subject satisfaction with treatment at twelve weeks using the 5-Point Likert Subject Satisfaction Scale 
Safety
 
Subject's assessment of discomfort and pain post-treatment as measured by the Wong-Baker Faces Pain rating scaleSubjects experiencing a treatment-related adverse event (AE)
POPULATION	The study will enroll up to 50 male and female subjects, 18 to 60 years of age who are seeking fat reduction of the abdomen.
PHASE	Pre-Market
NUMBER OF SITES	Up to 5 sites
DESCRIPTION OF DEVICE	The investigational device (Venus Bliss™) is a non-invasive medical aesthetic device designed for body contouring. The device is comprised of a console, four 1060 nm diode laser applicators (60 mm x 60 mm). A belt is included to allow the operator to secure the laser applicators on the lipolysis treatment area, allowing hands free operation.
STUDY DURATION	Twelve months
PARTICIPANT DURATION	Three months

SCHEMATIC OF STUDY DESIGN

2 INTRODUCTION: BACKGROUND INFORMATION AND SCIENTIFIC RATIONALE

2.1 BACKGROUND INFORMATION

There are multiple, non-invasive fat reduction procedures currently available for non-surgical body-contouring. Technologies include cryolipolysis, radiofrequency, high frequency focused ultrasound, and photobiomodulation. All modalities deliver some form of energy that creates changes in the adipocytes. Studies show that these therapies are safe and effective.

Many non-invasive laser technologies have been studied with the efficacy of laser therapy purported to be related to the wavelength and the energy delivered. Initial lasers studied include the neodymium-doped yttrium aluminum garnet (Nd:YAG) laser delivering 1064nm and 1320nm wavelengths. Diode lasers were introduced delivering energy at 980nm, 924nm, 975nm and 920nm wavelengths. The quest for the most effective laser diode wavelength for lipolysis with the least adverse effect continues, most recently with the 1060nm wavelength.

The 1060nm laser diode leads to the injury of the adipocytes through direct heating of the tissue. The energy delivered creates movement within the molecules of the exposed tissue, which then generates heat. A controlled temperature of 42-47 °C must be maintained at the site of adipocytes. At this temperature, the cell membranes of the adipocytes lose their structural integrity leading to cell death. Upon cell injury and death, the body naturally eliminates the contents of the adipocytes with results at 6 weeks but optimally at 12 weeks. The 1060nm wavelength has a particular affinity for adipocytes with low absorption within the dermis. In addition, melanin is minimally targeted so the device can be used in all skin types. (Schilling L et al)

This study will investigate whether a single treatment with a 1060nm laser delivered by the Venus Bliss™ investigational device is safe and efficacious for the reduction of abdominal fat. In addition, the study will investigate whether the effects of this single treatment are maintained at six months post-therapy.

2.2 RATIONALE

The use of 1060nm laser diode technology has been shown in clinical studies to be safe and effective for lipolysis. The objective of this clinical study is to evaluate the safety and efficacy of the use of the Venus Bliss™ investigational medical device for non-invasive fat reduction of the abdomen.

The use of the Venus Bliss™ has been determined to present non-significant risk in accordance with 21 CFR 812.3 for the intended use in this study, because the device is not:

- Intended as an implant;
- purported or represented to be for use supporting or sustaining human life;
- for use of substantial importance in diagnosing, curing, mitigating, or treating disease, or otherwise preventing impairment of human health; or
- Otherwise presenting a potential for serious risk to the health, safety, or welfare of a subject.

Furthermore, the use of the non-invasive 1060nm laser diode technology for lipolysis has been reported without incidents or significant complications by Bass LS et al, 2018; Decorato, JW et al, 2017 and Katz B et al, 2018.

This study will be conducted in compliance with the protocol and according to Good Clinical Practice (GCP) standards.

2.3 POTENTIAL RISKS AND BENEFITS

2.3.1 KNOWN POTENTIAL RISKS

Expected adverse events of the laser treatment procedure include transient tenderness, erythema, edema, and/or induration in the treated area lasting from one to three weeks after the treatment. In addition, other adverse events may include and include localized firmness, ecchymosis, skin burn, hyperpigmentation, hypopigmentation, blister and changes in skin laxity. Rarely, skin contour irregularities, dimpling, asymmetry (uneven appearance due to uneven anatomy or uneven treatment of the area), necrosis (tissue death), hardness and nodules occur. Protective laser eyewear will be worn by the subject and operator providing the procedure.

The device has a contact tissue cooling system in place during the procedure to minimize thermal discomfort and prevent damage to the treatment area. Expected adverse events related to the contact cooling include tingling, itching, decreased sensation, numbness, erythema and tenderness.

The boundaries of the treatment area will be marked with a semi-permanent tattoo ink using a microblade. The ink markings should dissipate within one year. Microblade marking may be associated with tenderness.

There are minimal risks associated with the use of ultrasound. The use of the ultrasound may cause redness of the skin. Skin rashes rarely occur with the use of ultrasound gel.

Risks will be mitigated by conducting this protocol with an investigator experienced in the therapeutic area of the clinical investigation. The investigator will be trained by the sponsor on the use of the device. The device design incorporates safety mechanisms which minimize risks. Patients will also be rigorously screened prior to their enrollment and rigorously followed over the course of the study.

2.3.2 KNOWN POTENTIAL BENEFITS

If the subject agrees to participate in this study, he/she will be contributing to the understanding of the safety and efficacy of the use of this investigational device for abdominal fat reduction. This

understanding may lead to optimization of the treatment with this device. In addition, the subject may benefit from reduction in unwanted adipocytes.

3 OBJECTIVES AND PURPOSE

The objective of this clinical study is to assess the safety and efficacy of using a 1060 nm diode laser for non-invasive fat reduction of the abdomen.

Primary objectives

- To determine proportion of independent, blinded reviewers who correctly identify pre-treatment baseline images and images taken at twelve weeks post-treatment

Secondary objectives

- To determine the change in thickness of the adipose layer as measured by ultrasound at twelve weeks post-treatment as compared to baseline
- To determine the change in abdominal circumference at twelve weeks post-treatment as compared to baseline
- To assess subject satisfaction with treatment at twelve weeks using the 5-Point Likert Subject Satisfaction Scale

Safety

- Subject's assessment of discomfort and pain post-treatment as measured by the Wong-Baker Faces Pain rating scale.
- Subjects experiencing a treatment-related adverse event (AE).

4 STUDY DESIGN AND ENDPOINTS

4.1 DESCRIPTION OF THE STUDY DESIGN

This is an open-label, baseline-controlled, evaluator-blind multi-center study evaluating one treatment with a 1060 nm diode laser for non-invasive fat reduction of the abdomen.

4.2.1 PRIMARY ENDPOINTS

- Photographic evaluation by independent, blinded reviewers with correct identification of pre-treatment baseline images when compared to post-treatment images taken at twelve weeks

4.2.2 SECONDARY ENDPOINTS

- To determine the change in thickness of the adipose layer as measured by ultrasound at twelve weeks post-treatment as compared to baseline
- To determine the change in abdominal circumference at twelve weeks post-treatment as compared to baseline
- To assess subject satisfaction with treatment at twelve weeks using the 5-Point Likert Subject Satisfaction Scale

Safety Endpoints:

- Report subject's assessment of discomfort and pain as measured by the Wong-Baker Faces Pain rating scale.
- Report subjects experiencing a treatment-related adverse event (AE).

5 STUDY ENROLLMENT AND WITHDRAWAL

5.1 PARTICIPANT INCLUSION CRITERIA

1. Able to read, understand and voluntarily provide written informed consent .
2. Healthy male or female, ≥ 18 years of age seeking treatment for unwanted fat in the abdomen.
3. BMI score is less than 30.
4. Agree to not making any major changes in their diet or lifestyle during the course of the study.
5. Able and willing to comply with the treatment/follow-up schedule and requirements.
6. Women of child-bearing age are required to be using a reliable method of birth control at least 3 months prior to study enrollment and for the duration of the study, and have a negative Urine Pregnancy test at baseline.

5.2 PARTICIPANT EXCLUSION CRITERIA

1. Pregnant in the last 3 months, intending to become pregnant, postpartum or nursing in the last 6 months.
2. Any previous liposuction/lipo-sculpture or any type of surgical procedure in the treatment area in the past 12 months.
3. History of immunosuppression/immune deficiency disorders (including AIDS and HIV infection) or use of immunosuppressive medications, 6 months prior to and during the course of the study.
4. History of hyperlipidemia, diabetes mellitus, hepatitis, blood coagulopathy or excessive bleeding.
5. Use of antiplatelet medications (81 mg acetylsalicylic acid daily permitted), anticoagulants, thrombolytics or anti-inflammatory medications within 2 weeks of treatment.
6. Having a history of skin cancer or any other cancer in the areas to be treated, including presence of malignant or pre-malignant pigmented lesions.
7. Having a permanent implant in the treatment area such as metal plates or an injected chemical substance such as silicone or parenteral gold therapy (gold sodium thiomolate).
8. Use of medications, herbs, food supplements, and vitamins known to induce photosensitivity to light exposure at the wavelength used or history of photosensitivity disorder.
9. Suffering from significant skin conditions in the treatment area or inflammatory skin conditions including but not limited to open lacerations, abrasions, herpes sores, cold sores, active infections.
10. Tattoos in the treatment area.
11. Poor skin quality (severe laxity).
12. Abdominal wall, muscular abnormality or hernia on physical examination.
13. Unstable weight within the last 6 months ($\pm 3\%$ weight change in the prior six months).
14. Use of retinoids such as oral isotretinoin (Accutane™) within the past six months or during course of the study.
15. Participation in another clinical study involving the same anatomical areas within the last 6 months.
16. History of keloid or hypertrophic scar formation or poor wound healing in the treatment area.
17. As per the investigator's discretion, any physical or mental condition which may make it unsafe for the subject to participate.

18. Unable or unlikely to refrain from sun exposure, artificial tanning, including the use of tanning booths, prior to (six weeks) and during the course of the evaluation.

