5.3 STRATEGIES FOR RECRUITMENT AND RETENTION

Up to 50 subjects will be enrolled at up to 5 sites. It is anticipated that it will take up to twelve months to complete the study. Subjects requesting non-invasive lipolysis of the abdomen will be recruited primarily from the investigator's clinic. Any advertising campaigns and materials will be reviewed and approved by an institutional review board (IRB) before implementation. Due to the duration of the study, subjects will be contacted by the investigative site on a regular basis in order to enhance retention.

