7.3 STUDY SCHEDULE

7.3.1 SCREENING

Screening Visit

If the subject meets the preliminary study criteria the study doctor, and/or his/her designee, will obtain an informed consent from the subject, clearly indicating his/her understanding of the requirements and possible risks involved with study participation and other applicable treatment options. Subjects will receive a unique identifying number that will be composed of a two-digit site number and a three digit subject number in sequence. This unique identifier will be used throughout the entire study and will be entered in the subject's case report form (CRF) and for each treatment.

During screening visit, the study investigator, and/or his/her designee, will assess the subject for eligibility to participate in the clinical study using the inclusion/exclusion criteria. A urine sample for the pregnancy test will be obtained for female subjects of child-bearing potential. During screening, the study doctor will review the subject's medical/surgical history and examine the target treatment areas to ensure they meet the study criteria.

Subjects will be instructed to avoid sun exposure of the target treatment areas for at least six weeks before treatment and to use broad spectrum sunscreen of no less than 30 SPF daily, replenishing it as often as needed throughout the course of the study and for six weeks after the treatment. In addition, tanning is to be strictly avoided. Subjects should not receive any treatment with a laser or other devices in the study treatment area throughout the course of this study and follow-up examinations.

The investigator will ask women of child-bearing potential for the date of their last period. The investigator shall inquire about the form of contraceptive they use to confirm they meet the inclusion criteria.

The subject will complete screening and the treatment will be scheduled. Treatment may be performed on the day the subject was enrolled if the results of the urine pregnancy test are available (and negative) and the subject has avoided sun exposure of the target treatment area for at least six weeks.

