7.6 PROHIBITED MEDICATIONS, TREATMENTS, AND PROCEDURES

The use of immunosuppressive medications, antiplatelet medications, thrombolytics, anti-inflammatory medications and anticoagulant medications is to be avoided. Herbal supplements, perfumes, cosmetics and/or medications that may affect sensitivity to light are prohibited. The use of Accutane™ (Isotretinoin) within the past six months is also strictly prohibited.

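### Recent commercial non-surgical fat reduction of the abdomen is not excluded, so in this baseline-controlled trial its delayed effect could be credited to the study laser if such subjects enrol

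*Combined protocol and SAP*

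**What the plan says.** Section 5.2 has two criteria on earlier interventions in the treatment area. Exclusion 2 reads "Any previous liposuction/lipo-sculpture or any type of surgical procedure in the treatment area in the past 12 months"; its closing words place it among surgical procedures. Exclusion 15 reads "Participation in another clinical study involving the same anatomical areas within the last 6 months", so it depends on trial participation, not on treatment received.

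Section 7.3.1 adds an instruction given at screening: "Subjects should not receive any treatment with a laser or other devices in the study treatment area throughout the course of this study". It looks forward only. The same section lets treatment take place on the day of enrolment if the pregnancy test is negative and sun has been avoided.

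Section 2.1 names the alternatives already on the market: "Technologies include cryolipolysis, radiofrequency, high frequency focused ultrasound, and photobiomodulation". For the 1060 nm laser it describes clearance of injured fat "with results at 6 weeks but optimally at 12 weeks". Section 5.3 states the source of subjects: "Subjects requesting non-invasive lipolysis of the abdomen will be recruited primarily from" the investigator's clinic.

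Section 10.6.1 confirms that there is no randomisation and that control is by baseline. The protocol summary says that twelve-week outcomes are compared with baseline.

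**The concern.** A subject treated commercially a few weeks before Visit 1 may still be losing fat at the treated site when the baseline photograph, ultrasound and circumference are taken. If so, part of the change seen at weeks 6 and 12 belongs to the earlier treatment. With no concurrent arm, the planned comparison cannot tell the two apart. Blinding the photograph reviewers does not help, because the later abdomen really is thinner.

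The photographic primary outcome and the ultrasound and circumference secondary outcomes are all exposed. The plan already treats earlier surgery (12 months) and an earlier study of the same area (6 months) as disqualifying. The closest equivalent of the study treatment is left out.

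**Working it through.** **Is the gap real?** I read all 6 inclusion and 18 exclusion criteria, together with Sections 7.3.1 and 7.6.

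| Provision | Covers recent commercial non-surgical treatment? |
|---|---|
| Exclusion 2 | No: liposuction, lipo-sculpture and surgery |
| Exclusion 13, "Unstable weight within the last 6 months" | No: body weight, not local fat |
| Exclusion 15 | Only if given inside another study |
| Exclusion 17 | No: conditions that make participation unsafe |
| Section 7.3.1 device ban | Only during the study |
| Section 7.6, which opens "The use of immunosuppressive medications, antiplatelet medications, thrombolytics, anti-inflammatory medications and anticoagulant medications is to be avoided" | No: medications, supplements, perfumes and cosmetics |

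The schedule of events labels screening as six weeks before treatment, but same-day treatment is allowed, so that label guarantees no interval. Even with a full six weeks under the device ban, a 1060 nm treatment given just before consent would have 12 − 6 = 6 weeks of its stated course left after Visit 1.

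**How large could the effect be?** The plan gives no figure for this. Inputs from Section 10.5 are an expected reduction of 2.65 (unit not stated), an SD of 1.41, read here as the SD of the change, and n = 40 as stated. Whether 40 follows from 2.65 and 1.41 is a separate question and does not affect this point. Two inputs are assumptions: *f*, the share of subjects recently treated, and *r*, the fraction of their 2.65 still to come after Visit 1. The value r = 50% is the average if time since treatment is spread evenly over 12 weeks and clearance is linear; r = 100% is the extreme.

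*Inflation of the mean ultrasound change* = f × r × 2.65:

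| f | r = 50% | r = 100% |
|---|---|---|
| 5% | 0.05 × 0.5 × 2.65 = 0.07 | 0.13 |
| 10% | 0.13 | 0.27 |
| 20% | 0.27 | 0.20 × 1 × 2.65 = 0.53 |

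*False rejection when the study laser has no effect* (two-sided 5% t-test, n = 40, noncentral t). The SD becomes √(1.41² + f(1−f)(r × 2.65)²). For f = 10% and r = 100% this is √(1.988 + 0.632) = 1.62, and the noncentrality is 0.265/1.62 × √40 = 1.03.

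| f | r = 50% | r = 100% |
|---|---|---|
| 5% | 0.059 | 0.084 |
| 10% | 0.086 | 0.173 |
| 20% | 0.192 | 0.458 |

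At f = 5% and r = 25% it is 0.052, essentially nominal.

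*Photographic criterion* (average of 80% correct, Section 10.4.2). Let p be the rate in the other subjects, and assume that recently treated subjects are always identified correctly. The overall rate is (1 − f)p + f. It reaches 80% at f = (0.80 − p)/(1 − p).

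| p | Overall rate at f = 5%, 10%, 20% | Break-even f | Subjects out of 50 |
|---|---|---|---|
| 78% | 79.1%, 80.2%, 82.4% | 0.02/0.22 = 9% | about 5 |
| 75% | 76.3%, 77.5%, 80.0% | 0.05/0.25 = 20% | 10 |
| 70% | 71.5%, 73.0%, 76.0% | 0.10/0.30 = 33% | about 17 |

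**The case against.** The strongest reply is that the exposure is hypothetical. A reader might infer from Section 5.3 that recently treated patients are common at these clinics. The section says only that subjects are asking for treatment, not that they have just had it. Someone treated within the last 12 weeks would have to want a second procedure before the first had taken full effect. This stands: the documents say nothing on frequency.

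Other parts of the reply also stand:

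- The 6-to-12-week course is stated for the 1060 nm laser. Applying it to cryolipolysis, radiofrequency or focused ultrasound is an assumption.
- A subject consented well ahead falls under the device ban from screening. That narrows the gap for that subject but does not close it, because same-day treatment is allowed.
- The calculation assumes that the earlier and study effects add fully in the same tissue. An already reduced area might respond less, so the net bias need not favour the device.
- At the planned effect the mean lies 2.65/(1.41/√40) ≈ 12 standard errors from zero. A shift of 0.07 to 0.53 would not change that test; it would affect the estimate.
- A reader might also infer that no analysis could remove the bias. That goes too far: if treatment dates are recorded, the affected subjects can be left out in a sensitivity analysis.

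The reply does not touch the gap itself. Medical and surgical history is taken at screening, but nothing ties a recent non-surgical treatment to eligibility or asks for its date, and no planned analysis separates such subjects.

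**Conclusion.** The point holds in conditional form. As written, the criteria admit a person with recent commercial non-surgical fat reduction of the abdomen. In an own-baseline design, any loss still in progress could be counted as study-laser effect.

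Confidence is high on the textual gap and low on its practical size, which depends on a share and a residual fraction that the documents do not give. Over the assumed range the ultrasound mean is inflated by 2.5% to 20% of the planned 2.65. Carry-over alone does not generally turn a failed photographic criterion into a pass: at a 75% underlying rate, a 10% share still gives 77.5%, a fail. It matters when the true rate is close to the threshold.

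This is a cheap improvement, not a flaw that invalidates the trial.

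**What to change.** Extend exclusion 2 or exclusion 15 to any non-surgical fat-reduction or body-contouring treatment of the abdomen, whether given inside or outside a study. The sponsor should choose the window and justify it. For this purpose it should at least cover the protocol's own 12-week response period; aligning it with the 6 months already in exclusion 15 would be one simple way. Add a dated question on such treatment to the medical and surgical history at screening.

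If enrolment has begun, collect the dates for subjects already treated. Repeat the photographic, ultrasound and circumference analyses without those treated inside the window, and report the results beside the main ones.

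The cost is one criterion line, one history item, an IRB amendment and the loss of a few otherwise eligible clinic patients.
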